4. LIST OF ABBREVIATIONS AND DEFINITIONS OF TERMS

Table 2: Abbreviations and Definitions

AE	adverse event
AESI	adverse event of special interest
AML	acute myeloid leukemia
BFI	Brief Fatigue Inventory
BLRM	Bayesian logistic regression model
CHF	congestive heart failure
DLT	dose-limiting toxicities
EAS	efficacy evaluable analysis set
ECG	electrocardiography
ECHO	echocardiography
ECOG	Eastern Cooperative Oncology Group
eCRF	electronic case report form
EPO	erythropoietin
ESA	erythropoiesis stimulating agents
EWOC	escalation with overdose control
FDA	Food and Drug Administration
GCP	Good Clinical Practice
GLP	Good Laboratory Practice
HNSTD	Highest Non-Severely Toxic Dose
ICH	International Conference on Harmonization
IEC	Independent Ethics Committee
IPSS-R	Revised International Prognostic Scoring System
IRB	Institutional Review Board
K-M	Kaplan-Meier
LVEF	left ventricular ejection fraction
MAD	maximum administered dose
MDS	myelodysplastic syndromes
MRI	magnetic resonance imaging
MTD	maximum tolerated dose
MUGA	multiple-gated acquisition
NYHA	New York Heart Association
PBMC	peripheral blood mononuclear cell
PI	Principal Investigator
PK	pharmacokinetic
PTT	partial thromboplastin time
RP2D	Recommended Phase 2 Dose
SAE	serious adverse event

SDP Oncology	Sumitomo Dainippon Pharma Oncology, Inc.
SRC	Safety Review Committee
STR	soluble transferrin receptor
TGF- β	transforming growth factor beta
TEAE	treatment-emergent adverse event
TIBC	total iron binding capacity
US	United States

5. INTRODUCTION

5.1. Disease Background

Myelodysplastic disease syndromes (MDS) is composed of a heterogeneous group of hematopoietic stem cell disorders and is characterized by dysplasia in 1 to 3 of the bone marrow cell lineages, either myeloid, megakaryocytic and/or erythroid lineages. The abnormal cells seen in MDS represent a malignant hematopoietic clone, which represses the remaining normal hematopoietic cells in the bone marrow. Patients with MDS have one or more significant peripheral blood cytopenias (anemia, leukopenia and/or thrombocytopenia).

The overall incidence of MDS in the general population is estimated to be 3 to 4 cases per 100,000 persons per year. Greater than 85% of these patients are older than 60 years at the time of diagnosis. It is also generally assumed that the incidence of MDS is underestimated due to the complexity of diagnosis. Indolent forms of MDS are often not clinically recognized or not evaluated due to patient comorbid conditions. In addition, a number of other disorders, including nutritional deficiencies, infections or medications, may cause transient cytopenias, without clonal aberrations. Bone marrow aspiration and biopsy including conventional cytogenetics is essential for diagnosis. Cytogenetic abnormalities are found in approximately 50% of MDS patients. Evaluation of peripheral blood or bone marrow for MDS-associated gene mutations may establish the presence of clonal hematopoiesis and help exclude benign causes of cytopenias, however do not in isolation establish a diagnosis of MDS.

The spectrum of MDS ranges from indolent disease in the low to intermediate risk category to severe bone marrow failure in those with high-risk disease resulting in life-threatening complications. Progression to acute myeloid leukemia (AML) occurs in about 30% of patients. The diagnosis is made by review of bone marrow aspirate revealing dysplastic marrow cellular changes that may include elevated blast counts and cytogenetic abnormalities. About 30% of patients diagnosed with low risk MDS progress to AML.

Anemia is common in patients with MDS reflecting ineffective erythropoiesis. Proinflammatory cytokines have long been implicated in the death of bone marrow progenitors in MDS ([Sallman, Blood 2019; 133\(10\):1039-1048](#)). Interleukin-6 and other cytokines of chronic inflammation lead to iron-restricted hematopoiesis ([Hematologica 2020; 105\(2\): 1-13](#)). Treatment options for anemia in MDS patients are limited (e.g., the administration of erythropoietic agents [EPO]) and are only beneficial to a sub-group of patients. As a consequence, ~ 70% of patients with low risk MDS require RBC transfusions and subsequently become transfusion dependent.

Clinical iron overload starts to develop in MDS patients before they become transfusion dependent because their ineffective erythropoiesis suppresses hepcidin production in the liver leading to unrestrained intestinal iron uptake. ([Santini V PLoS ONE: 2011;6\(8\)](#)). However, the most important cause of iron overload in MDS is chronic transfusion therapy. While transfusion dependency by itself is a negative prognostic factor reflecting poor bone marrow function, the ensuing transfusion and dose dependent iron overload have an additional negative impact on the survival of patients with low to intermediate risk MDS due to the complications of bone marrow failure or acute leukemia ([Malcovati L 2011](#)).

The Myelodysplastic Syndromes (MDS) Event Free Survival With Iron Chelation Therapy trial (TELESTO) was the first placebo-controlled study evaluating outcomes using iron chelation

therapy in low risk MDS. Results presented in 2018 showed a 36.4% risk reduction in event-free survival in chelated patients, fewer cardiac and liver-related events and fewer progression events to AML compared with placebo. ([Angelucci et al, Blood \(2018\); 132 Supplement 1: 234.](#))

There are 3 approved chelating agents for the treatment of iron overload (deferoxamine, deferasirox, and deferiprone). However, these agents have limited efficacy and are associated with adverse effects.

The management of anemia in MDS remains a challenging issue for hematologists/oncologists. This population is primarily elderly with significant co-morbidities making them relatively intolerant to therapy. Few therapeutic products have been approved to treat lower risk MDS. Revlimid® (lenalidomide) is approved by the United States (US) Food and Drug Administration (FDA), but only in subjects with transfusion dependent anemia due to low, or intermediate risk MDS and with a 5q deletion abnormality. The approved label for Revlimid bears a black box warning due to significant risks associated with its treatment including thrombocytopenia and neutropenia, embryofetal toxicity, and incidences of renal and hepatic toxicities (USPI Revlimid). Reblozyl® (luspatercept) was recently approved for the treatment of anemia in adult patients with very low- to intermediate MDS with ring sideroblasts (MDS-RS) or with myelodysplastic/myeloproliferative neoplasm with ring sideroblasts and thrombocytosis (MDS/MPN-RS-T) who have failed an erythropoiesis stimulating agent (ESA) and require at least 2 red blood cell units over 8 weeks. Options for treating anemia in lower risk MDS remains an unmet need.

5.2. Rationale for Study

The ineffective hematopoiesis present in MDS has long been considered to be related to inflammatory cytokines, including the TGF- β pathway associated with SMAD2/3 signaling (Herbertz 2010). The natural inhibitor of the TGF- β /SMAD2/3 signaling pathway, SMAD7, is suppressed in MDS progenitor cells due to increased miR21 expression, which in turn upregulates the TGF- β /SMAD2/3 pathway with subsequent suppression of hematopoiesis (Bhagat 2013). This leads to increased expression of myelosuppressive cytokines and decreased burst forming unit-erythroid (BFU-E) and colony forming unit- granulocyte, erythrocyte, monocyte, megakaryocyte (CFU-GEMM). These same cytokines are immunosuppressive and may also contribute to the fatigue seen in MDS patients. Blockade of the TGF- β /SMAD2/3 pathway with an TGF- β R1/ALK-5 inhibitor may improve the ineffective erythropoiesis seen in MDS and offer therapeutic benefit for the treatment of MDS.

TP-0184 is a small molecule dual inhibitor against ALK-2 and ALK-5, affecting both ALK-2-SMAD1/5/8 and ALK5-SMAD2/3 signaling pathways, respectively. In pre-clinical studies TP-0184 was shown to inhibit downstream signaling from ALK-2 kinase (by reducing phospho SMAD1/5 levels) in cancer cells treated with the ALK-2 ligand BMP2, and to block expression of hepcidin, an important regulator of iron levels, and thus erythropoiesis. Hepcidin was found to be a responsive biomarker to ALK-2 inhibition in cancer cell culture models. Hepcidin was also found to be a pharmacodynamic biomarker in in vivo studies with liver tissue and blood in the mouse model with acute inflammation or bacteria-induced anemia. Due to the lack of an appropriate in vivo model for MDS, the role of hepcidin in the anemia due to MDS is unknown. However, it may or may not play a role as a part of the ALK-2 signaling pathway effecting the anemia due to MDS. TP-0184 was also determined to be a potent inhibitor of

TGF β R1/ALK-5 ex-vivo studies. This was demonstrated by TP-0184 inhibiting downstream signaling from ALK-5 kinase by reducing SMAD2/3 phosphorylation in cancer cell lines treated with the ALK-5 ligands, TGF β and GDF11, the growth factors leading to altered hematopoietic differentiation in MDS (Zhou L 2008). TP-0184 was found to inhibit ALK-5 pathways and SMAD2/3 phosphorylation in reporter assays at sub-micromolar to single digit micromolar concentrations. Activity of TP-0184 with in-vitro cellular models was similar to other known ALK-5 inhibitors. Though in vivo studies evaluating ALK-5 inhibition by TP-0184 have not been conducted to date, erythroid colony counts in the bone marrow and erythropoietic markers such as hemoglobin were found to be responsive biomarkers to ALK-5 inhibition in a transgenic mouse model for MDS by other ALK-5 inhibitors (eg, galunisertib) (Zhou L 2014). The in vitro and in vivo pharmacology data and the inhibitory activity of TP-0184 towards both the ALK-5 and ALK-2 signaling pathways supports the proposed evaluation of treatment of anemia in MDS patients with TP-0184.

To conclude, the inhibition of both ALK-2 and ALK-5 pathways by TP-0184 presents a potential option for the treatment of anemia due to MDS. Treatment with TP-0184 may result in the reduction of ineffective erythropoiesis and offer therapeutic benefits of improving anemia and lowering the frequency of transfusions. This, in turn, will lower the risk of iron overload.

5.3. Summary of Risks and Benefits in Humans

A full summary of risks and benefits in humans is included in Section 6, Data and Guidance for Investigators, of the Investigator Brochure.

5.4. Investigational Product Background

5.4.1. Nonclinical Studies

Twenty-eight-day repeat-dose Good Laboratory Practice (GLP) toxicology and toxicokinetic studies were conducted in rats and dogs.

Rats were given TP-0184 orally, once-daily at 0 (vehicle), 20, 50, and 150 mg/kg/day (human equivalents of 120, 300 and 900 mg/m²/day, respectively), and following the last dose a subset of rats was held for a 14-day post-treatment recovery period. Rats given 150 mg/kg/day lost weight (or gained less weight than controls). At the end of the dosing period, rats given 150 mg/kg/day had slightly higher ALT and AST compared with controls. At necropsy, liver weights were higher than controls for rats given 50 or 150 mg/kg/day. All TP-0184-treated groups exhibited mild, pan-lobular hepatocellular hypertrophy as well as lymph node sinus erythrocytosis; the incidence was dose-related. At the end of the recovery period, chemistry parameters as well as liver and lymph node morphology were normal. The Severely Toxic Dose in 10% of the animals (STD10) was determined to be greater than 150 mg/kg/day.

Dogs were given TP-0184 orally, once-daily at 0 (empty capsules), 2, 5, and 10 mg/kg/day (human equivalents of 40, 100, and 200 mg/m²/day), and following the last dose a subset of dogs was held for a 14-day post-treatment recovery period. One dog given 10 mg/kg/day was euthanized because of poor condition near the end of the study: it had pronounced clinical signs (emesis, mucoid/ soft feces, diarrhea), lost substantial weight and consumed less food, and did not respond to veterinary intervention. Emesis occurred in all treatment groups and incidence was dose-related; at 5 or 10 mg/kg/day, weight loss as well as diarrhea/ soft feces also occurred

along with decreased food consumption. During the recovery period dogs did not exhibit treatment-related clinical signs, and weight gain and food consumption were similar among control and treated groups. There were no treatment-related gross or microscopic pathologic findings. The Highest Non-Severely Toxic Dose (HNSTD) was determined to be greater than 5 mg/kg/day.

For additional details regarding these studies, please refer to the TP-0184 Investigator Brochure.

5.4.2. Clinical Studies

5.4.2.1. Study TP-0184-101 (Solid Tumor)

The first in human clinical study of TP-0184 (Tolero Study No. TP-0184-101) is ongoing in adult patients with advanced/refractory solid tumors. Since the study is still ongoing, a complete evaluation of the safety of this compound given in escalating doses has not yet been conducted.

At the start of this study, a Phase 1 first-in-human study exploring escalating dose levels of TP-0184 in patients with advanced solid tumors had already been initiated with a starting dose of 30 mg QD for 21 days. Subsequently, dosing was changed to once weekly, with a starting dose of 60 mg once weekly for 4 weeks (Amendment 2, 12 Sep 2019). The most common side effects, regardless of causality, were gastrointestinal (nausea, vomiting) and fatigue. There were no clinically significant trends of hepatic or cardiac toxicity and the safety profile was considered favorable. Preliminary PK analysis suggested dose-related increases in systemic exposure with increasing dose and longer elimination $t_{1/2}$ than projected from preclinical PK data. Please refer to the TP-0184 Investigational Brochure for additional information.

Changes in cardiac valve status have been documented in in vivo pre-clinical studies (not human) with small molecule kinase inhibitors in the same therapeutic class as TP-0184.

Following discussion with the US FDA, cardiac toxicity and hepatotoxicity were identified as Adverse Events of Special Interest (AESIs) in Study TP-0184-101. While there have been some changes in cardiac markers (BNP, NT-proBNP) observed on study, the changes have been either Grade 1 or Grade 2 in severity, and none have been associated with clinical symptoms or notable changes in ejection fraction. Thus far, no clinically significant trends of hepatic or cardiac toxicity have been reported.

5.4.2.2. Study BBI-TP-0184-102 (MDS)

Patients with MDS related anemia frequently require chronic RBC transfusions, which may cause iron overload. The potential for deposition of iron in the heart and liver may lead to organ dysfunction. Iron overload has an additional dose dependent negative impact on the survival of patients with lower risk MDS. Treatment with an ALK-2/ALK-5 inhibitor could result in improvement of anemia, resulting in fewer transfusions and may thereby reduce the risk of iron overload. The risk of potential iron deposition and its sequelae on the heart and liver is reduced by intensive cardiac and hepatic monitoring as a proactive strategy to avoid undue toxicity.

Study BBI-TP-0184-102 contains several measures to ensure patient safety, such as defined patient selection criteria for participation, judicious and gradual dose escalation rules, appropriate safety surveillance measures, and comprehensive dose modification guidelines to be implemented in case of treatment toxicity. In addition to physical examinations and routine laboratory testing, the medical assessments used in this study to evaluate safety include

comprehensive cardiac monitoring with intensive ECG (with QTcF assessment in Phase 1), cardiac MRIs for iron quantification, echocardiography/MUGA scans, laboratory markers for heart failure (BNP, NT-proBNP), and safety ECGs. Based on the mechanism of action of TP-0184, cardiac toxicity and hepatotoxicity events will be captured as AESIs in this study.

Liver monitoring includes liver function testing and hepatic MRIs for iron quantification. Iron panels (including ferritin) are performed frequently throughout the study per protocol.

Blood tests will also be used to explore molecular markers associated with the biology of MDS and the mechanism of action of TP-0184. These biomarkers will not be used to make therapeutic decisions on dosing or regimen management; they are only conducted for experimental purposes, to gain a better understanding of the biology of the treatment at the cellular and molecular levels, and to evidence pharmacodynamic action.

The protocol minimizes currently known risks of TP-0184 by frequent monitoring for early detection of AEs. Given the anticipated benefits of TP-0184, the safety profile of TP-0184 in patients treated in this study is considered favorable. Results of this study could contribute to a better understanding, treatment, evaluation, and management of future patients affected by MDS and anemia of cancer.

More detailed information about the known and expected benefits and risks may be found in the Investigator's Brochure.

6. STUDY OBJECTIVES AND ENDPOINTS

6.1. Primary Objectives and Endpoints

Primary Objectives	Study Endpoints
Phase 1	

 • To assess the safety and tolerability of TP-0184 • To determine the maximum tolerated dose (MTD) or maximum administered dose (MAD) and recommended dose for the future expansion arms of TP-0184 in the Phase 2 part of the study 	Assessment of dose limiting toxicities (DLTs), treatment-emergent adverse events (TEAEs); type, frequency and severity of AEs and relationship of AEs to TP-0184, TP-0184 dose interruptions and dose reductions
Phase 2	
To determine the effect of TP-0184 on the treatment and the hematologic improvement of anemia in terms of hemoglobin increase, reduction in RBC transfusions and Transfusion-Free \geq 8 weeks	
Response rate based on composite response criteria:
 
Hemoglobin increase \geq 1.5 g/dL maintained for a consecutive period of 8 weeks with no transfusions
 
OR
 
Reduction in units of \geq 4 RBC transfusions / 8 weeks (consecutive) compared with the pretreatment transfusion number in previous 8 weeks
 
OR
 
Patients who are RBC transfusion-free over any consecutive 8-week (56-day) period

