8. SELECTION AND WITHDRAWAL OF PATIENTS

8.1. Inclusion Criteria

Each patient must meet the following criteria to be enrolled in this study:

1. A documented diagnosis of lower risk MDS (IPSS-R Low, Intermediate) according to WHO 2016 classification, de novo or secondary.
2. Bone marrow biopsy and/or aspirate performed pre-dose to assess disease status and available for review *prior* to full screening review. If the bone marrow biopsy and/or aspirate is nonproductive or nondiagnostic, the procedure must be repeated. Bone marrow biopsy/aspirate performed \leq 12 weeks prior to baseline will not need to be repeated if results and a minimum of 6 slides are available.
3. Relapsed, refractory/resistant, intolerant, or inadequate response to ESA treatment, as defined by the following:
 - Relapse according to IWG 2006
 - Refractory/resistant – documented non-response or response that is no longer maintained to prior ESA-containing regimen, either as single agent or combination (eg, with G-CSF). ESA regimen must have been either:
 - Recombinant human erythropoietin (rHu EPO) \geq 500 IU/wk for at least 8 doses or equivalent

OR

 - Darbepoetin alpha \geq 300 μ g Q3W for at least 4 doses or equivalent
 - Intolerant – documented discontinuation of prior ESA containing regimen, either as single agent or combination (eg, with G-CSF), at any time after introduction due to intolerance or an adverse event.
 - Inadequate response – in the absence of transfusions support, patients under ESA treatment for at least 12 weeks that do not show a rise in hemoglobin of greater than equal to 1 g/dl.
4. Patients with 5q deletions are allowed only if they have failed or are intolerant to lenalidomide treatment.
 - Failure or intolerance to lenalidomide defined as clinical and cytogenetic responses to according to the international working group 2006 MDS: (1) absence of response; (2) bone marrow progression during treatment with or without prior response; (3) secondary failure (loss of prior hematological response without bone marrow progression); or, (4) intolerance (treatment discontinuation due to AEs, with or without prior response) based on investigator judgement ([Prebet 2017](#)).
5. Previous treatment for anemia with or without RBC transfusion support:
 - a. Low transfusion burden (LTb), defined as requiring less than 4 red blood cell units in the 8 weeks before treatment (and baseline hemoglobin $<$ 9.0 g/dL)

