13.1.9.1.2. Phase 2 Efficacy Analysis

13.1.9.1.2.1. Response Rate

Response rate is defined as the proportion of patients who achieves response according to the composite endpoint criteria for a consecutive period of 8 weeks ([Appendix 1](#)). Response rate will be estimated with 2-sided 95% exact binomial confidence intervals based on EAS.

13.1.9.1.2.2.12-Week Response Rate

The 12-Week response rate is defined as the proportion of patients who achieves response according to the composite endpoint criteria for a consecutive period of 12 weeks ([Appendix 1](#)). The 12-Week response rate will be estimated with 2-sided 95% exact binomial confidence intervals based on the EAS.

13.1.9.1.2.3. Time to RBC transfusion-free analysis

Time to RBC transfusion-free period is defined as the time from the date of initial dosing at RP2D to first documentation of a transfusion-free period for patients who have one or more transfusion-free periods. Transfusion-free period is defined as the period that a patient becomes transfusion-free for consecutive 8 weeks or longer after treatment of TP-0184. Kaplan-Meier (K-M) survival curve and K-M median (estimate), along with 2-sided 95% CIs, will be provided.

13.1.9.1.2.4. Duration of Hemoglobin Response

Duration of hemoglobin response is defined as the time from the date of first documentation of a hemoglobin response to the date of first documentation of progression of hemoglobin response for hematologic responders. Hemoglobin response is defined as an increase ≥ 1.5 g/dL maintained for a consecutive period of > 8 weeks with no transfusions; hemoglobin progression is defined as a change from baseline < 1.5 g/dL of the hemoglobin or the start of one or more transfusions.

The K-M survival curve and K-M median (estimate), along with 2-sided 95% CIs will be provided.

13.1.9.1.2.5. Duration of Reduction in RBC Transfusion for 8 Weeks Analysis

High transfusion burden patient with reduction in RBC transfusion for 8 weeks is defined as high transfusion burden patients (baseline ≥ 4 U transfusions) patients with change from baseline of equal or more than 4 units transfusions in consecutive 8 weeks in EAS.

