Duration of reduction in RBC transfusions for 8 weeks is defined as the time from the assessment date of consecutive 8 weeks with reduction from baseline of RBC transfusions ≥ 4 units to the assessment date of the reduction from baseline < 4 units or increased transfusions frequencies from baseline within a consecutive 8 weeks. For high transfusion burden patient with reduction in RBC transfusion.

The K-M survival curve and K-M median (estimate), along with 2-sided 95% CIs will be provided.

13.1.9.1.2.6. Duration of RBC Transfusion-Free Period ≥ 8 weeks

RBC transfusion-free period ≥ 8 weeks patient is defined as a patient who maintains RBC transfusion-free during consecutive 8 weeks or longer in EAS.

Duration of RBC transfusion-free period ≥ 8 weeks is defined as the time from the assessment date of consecutive 8 weeks without any RBC transfusions to the assessment date of the first documented transfusion in the following visits for RBC transfusion-free period ≥ 8 weeks patients.

The K-M survival curve and K-M median (estimate), along with 2-sided 95% CIs will be provided.

13.1.9.1.2.7. Changes in Neutrophil Count

Hematologic improvement in neutrophil count (HI-N) is defined as patients achieving over any consecutive 8-week (56-day) period and / or decrease in neutrophil levels in EAS.

Change in neutrophils analysis will provide summary statistics of the proportion of patients with hematologic improvement in neutrophil count with 2-sided 95% exact binomial confidence intervals using EAS.

13.1.9.1.2.8. Changes in Platelet Count

Hematologic improvement in platelet count (HI-P) is defined as patients achieving hematologic improvement in platelets over any consecutive 8-week (56-day) period and / or decrease in platelet levels in EAS.

Change in platelet count analysis will provide summary statistics of the proportion of patients with hematologic improvement in platelet count with 2-sided 95% exact binomial confidence intervals using EAS.

13.1.9.1.2.9. Progression to AML

Progression to AML is defined follow the guidelines by IWG Response Criteria for MDS 2006 ([Appendix 6](#)).

Summary statistics of the proportion of patients progressing to AML will be estimated with 2-sided 95% exact binomial confidence intervals based on EAS.

13.1.9.1.2.10. Time to Progression to AML

Time to progression to AML is defined as the time from the date of initial dosing at RP2D to the date of first documented progression to AML using EAS.

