20. APPENDICES

**APPENDIX 1. CONSIDERATION OF RESPONSE FOR COMPOSITE
ENDPOINT**

Patient population	Hemoglobin increase ≥ 1.5 in the absence of transfusion / 8 weeks	RBC transfusion free / 8 weeks	Reduction in units of ≥ 4 RBC transfusions / 8 weeks
High transfusion burden (≥ 4 U transfusion)	X	X	X
Low transfusion burden (1-3 U transfusion)	X	X	

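### Patients with 0 RBC units at baseline are eligible and count as responders just for staying untransfused, and Appendix 1 has no row for them

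*Protocol*

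**What the plan says.** **Eligibility.** Inclusion criterion 5 in protocol Section 8.1 (repeated in the synopsis) reads "Previous treatment for anemia with or without RBC transfusion support". Low transfusion burden is "defined as requiring less than 4 red blood cell units in the 8 weeks before treatment", together with a baseline hemoglobin below 9.0 g/dL. No lower bound on units is set. Criterion 6 asks for a 12-week transfusion record, not for a minimum number of units. The inadequate-response route in criterion 3 describes ESA-treated patients without transfusion support.

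**Primary endpoint.** Section 6.1 joins three criteria with OR: a hemoglobin rise of at least 1.5 g/dL held for 8 weeks without transfusion; a fall of at least 4 units per 8 weeks from the pretreatment count; and "Patients who are RBC transfusion-free over any consecutive 8-week (56-day) period". The third has no baseline condition. The synopsis and SAP Section 1.2 repeat it, and Section 6.2 has a 12-week version.

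**Analysis.** Section 13.1.9.1.2.1 defines the response rate as "the proportion of patients who achieves response according to the composite endpoint criteria for a consecutive period of 8 weeks" and cites Appendix 1. Section 13.1.9.1.2.2 cites the same appendix for response "according to the composite endpoint criteria for a consecutive period of 12 weeks". Appendix 1 has one row for 4 or more units and one labelled "Low transfusion burden (1-3 U transfusion", with all columns per 8 weeks. The efficacy evaluable set (Section 13.1.5) does not exclude 0-unit patients. Section 13.1.3 calls the study successful if Prob(θ ≥ 0.20) > 0.50 at about 60 evaluable patients.

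**The concern.** For a patient with 0 units at baseline, 8 weeks without transfusion is no change, yet Section 6.1 scores it as response. The stated objective is hematologic improvement of anemia. With no control arm and a fixed 20% benchmark, each such patient adds to the success count, and nothing in the design offsets the bias.

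Appendix 1 does not settle the matter. Read literally, it marks no criterion for a 0-unit patient, so even a sustained 1.5 g/dL rise would not count. If the patient is placed in the low-burden row instead, the transfusion-free column applies and the result is the same as under Section 6.1. Two analysts could therefore report different response rates from the same data.

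The time-to-event endpoints have the same gap. Section 13.1.9.1.2.3 rests on "the period that a patient becomes transfusion-free for consecutive 8 weeks or longer after treatment of TP-0184" and Section 13.1.9.1.2.6 on "a patient who maintains RBC transfusion-free during consecutive 8 weeks or longer in EAS"; neither states a baseline requirement.

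**Working it through.** **1. Follow one patient through the text.** Take 0 units in the 8 weeks before treatment, hemoglobin below 9.0 g/dL, no transfusion and no hemoglobin gain on study.

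| Place | Outcome |
|---|---|
| Section 8.1, criterion 5 | Eligible, low burden |
| Section 13.1.5, EAS | In the denominator |
| Section 6.1 | Responder (third criterion) |
| Appendix 1, read literally | No row, no criterion |
| Appendix 1, placed in low-burden row | Responder |
| Appendix 6, IWG 2006 erythroid response | Not a responder (needs a 1.5 g/dL rise or a 4-unit reduction) |

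The hemoglobin criterion in Section 6.1 itself requires 8 weeks without transfusion. Anyone who meets it already meets the third criterion, so it adds no responder.

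**2. Cut-off for final success.** The documents state no prior, power or type I error for Phase 2, so there is no figure of the plan's own to reproduce. Three priors are assumed. The cut-off is the smallest x with Prob(θ ≥ 0.20 | x of 60) > 0.50.

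| Prior | Posterior probability just below the cut-off | At the cut-off |
|---|---|---|
| Beta(1,1) | x = 11: 0.424 | x = 12: 0.551 |
| Beta(0.5,0.5) | x = 11: 0.385 | x = 12: 0.513 |
| Beta(0.2,0.8) | x = 12: 0.474 | x = 13: 0.601 |

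**3. Apparent response rate.** Let s be the share at 0 units, q the share of those who have 8 weeks untransfused on study, r the response rate in everyone else, and h the hemoglobin response rate in 0-unit patients. All are assumptions.

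- Section 6.1 reading: p = s·q + (1 − s)·r
- 0-unit patients as non-responders: p = (1 − s)·r
- Proposed rule: p = s·h + (1 − s)·r, with h = r, so p = r

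Example with s = 0.20, q = 0.75, r = 0.05: p = 0.15 + 0.04 = 0.19.

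**4. Probability of final success.** P(X ≥ 13) to P(X ≥ 12), with X ~ Bin(60, p) and early stopping ignored.

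| s | r | q = 50% | q = 75% | q = 100% | Proposed rule |
|---|---|---|---|---|---|
| 0.10 | 0.05 | 0.004-0.010 (p = 0.095) | 0.02-0.05 (0.12) | 0.09-0.15 (0.145) | <0.001 |
| 0.20 | 0.05 | 0.07-0.13 (0.14) | 0.35-0.47 (0.19) | 0.71-0.81 (0.24) | <0.001 |
| 0.30 | 0.05 | 0.31-0.43 (0.185) | 0.82-0.89 (0.26) | 0.98-0.99 (0.335) | <0.001 |
| 0.20 | 0.10 | 0.28-0.39 (0.18) | 0.65-0.76 (0.23) | 0.89-0.94 (0.28) | 0.006-0.015 |

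At s = 0.20, r = 0.05 and q = 25% (p = 0.09) the figure is 0.002-0.007. Counting 0-unit patients as non-responders gives <0.001 at r = 0.05 (p = 0.04) and 0.001-0.003 at r = 0.10 (p = 0.08).

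**5. Break-even.** If the others respond at 5%, the share of all evaluable patients who are both at 0 units and stay untransfused that brings the apparent rate to 20% is (0.20 − 0.05)/0.95 = 15.8%.

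**6. With monitoring.** Section 13.1.9 allows stopping from 10 evaluable patients. With both stopping rules applied after every patient from 10 to 60, the probability of any success is 0.16-0.28 at p = 0.14 and 0.76-0.87 at p = 0.24, against 0.003-0.013 at p = 0.05.

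**The case against.** **Sizes.** The share s, the proportion q and the prior have no source in the documents. Every eligible 0-unit patient has hemoglobin below 9.0 g/dL, so many may need transfusion and q could be low. That is fair. It affects q only, and at q = 25% the effect is small, as shown.

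**Chance gaps in the 1-3 unit group.** A low value of r for everyone else understates responses that arise without drug effect. If transfusion events follow a Poisson process over 24 weeks, the chance of some 56-day gap is about 0.90, 0.60 and 0.33 at 1, 2 and 3 events per 8 weeks. Take 20%, 40% and 40% of patients at 0, 1-3 and 4 or more units, with 5% response in the first and last groups. If 36% of the middle group have a chance gap, p = 0.01 + 0.144 + 0.02 = 0.174 and the proposed rule still passes with probability 0.24-0.35. At 50%, p = 0.23 and it passes with 0.65-0.76. This stands: the fix removes the 0-unit problem, not this one, and the values below 0.001 hold only if r is really that low.

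**Wording.** The phrase about becoming transfusion-free in Section 13.1.9.1.2.3 may hint at prior transfusion, but it sets no such condition. The IWG comparison is also limited: those criteria have no transfusion-free limb for any patient, so they do not by themselves yield a 1-unit threshold.

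**Relevance.** SAP Section 2 records termination after two patients, with listings only. No success rule will be applied. That limits the consequence but does not make the definition sound.

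**Conclusion.** The concern holds as stated. Section 8.1 admits 0-unit patients, Section 6.1 makes them responders for no change, Appendix 1 omits them, and neither the EAS definition nor the SAP closes the gap. The text alone establishes this.

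The main risk is an inflated response rate. The opposite reading (no row, so no response) is less likely but is not excluded. The size depends on assumed case mix and prior: negligible if few patients have 0 units or few of them stay untransfused, and large enough to decide the trial once about one patient in six is both. This should be fixed in the design. It alters no reported result.

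**What to change.** Reconcile Sections 6.1 and 8.1 and Appendix 1, and carry the change into the synopsis, Section 6.2 and SAP Section 1.2.

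- Apply the transfusion-free criterion only to patients with at least 1 RBC unit in the matching pretreatment period: 8 weeks for the 8-week endpoint, 12 weeks for the 12-week endpoint. Write the 12-week condition out, since the Appendix 1 columns are per 8 weeks only.
- Add a 0-unit row to Appendix 1 judged on the hemoglobin criterion alone. Leave the other two rows unchanged.
- Put the same baseline condition on the time to, and the duration of, the transfusion-free period.
- Report response by baseline burden (0, 1-3, 4 or more units) and by component, and state that chance 8-week gaps in 1-3 unit patients remain a limitation.

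**Cost.** An amendment to the endpoint wording and one table row. Baseline hemoglobin and the 12-week transfusion count are already required for the EAS. The response rate will be somewhat lower than under Section 6.1. A patient with 0 units in the last 8 weeks but some in weeks 9-12 before dosing could qualify on the transfusion-free criterion at 12 weeks and not at 8, so the two endpoints are not fully nested; a table note should say so.
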